Subjects with less than 70 reduction in the CDAI (non-responders) at evaluation in Week 12 are to move on to the rescue period. The rescue period is to last 12 weeks, with additional administrations of 10 mg/kg of E6011 in Week 12, Week 13, Week 14 and every two subsequent weeks up to Week 22. Subjects with a reduction in the CDAI of 70 or more compared to baseline/Week 12 at evaluation in Week 24 of the rescue period are to move on to the open-label extension period. The extension period is to last 40 weeks, with 10 mg/kg of E6011 administered every four weeks from Week 24 to Week 60 and E6011 efficacy is to be evaluated at Week 64. Patients with less than 70 reduction in the CDAI compared to baseline and Week 12 at evaluation in Week 24 are to be discontinued.

[figure not shown]
The Principal Investigator or Sub-investigator is to confirm that the subjects' data as of Week 12 of the remission-induction period (double-blind) has been completely entered into the eCRF by the time the first evaluation in the rescue period or extension period takes place. Blinding in the double-blind period is to be maintained until a database in the double-blind study period is locked.

The post-observation period consists of an assessment in person 28 days after the completion or discontinuation of the extension period of the clinical trial, and an assessment in person or over the phone 70 days after the last administration of the IMP. The follow-up period entails contacting the patients over the phone, etc. every 6 months until 2 years have passed from the last administration of the IMP to inquire whether they have experienced progressive multifocal leukoencephalopathy (PML).

Date: 18-Apr-2022 version 11.0 Confidential Page 25 of 80

Figure 1 shows the design of the clinical trial.

Figure 1 Clinical trial design

Responders at CDAI evaluation on Week 12 of the remission-induction period are to move on to the extension period, in which E6011 is administered every four weeks. Non-responders are to move on to the rescue period, and if the CDAI has improved by Week 24, they are to move on to the extension period, in which E6011 administered every four weeks. Subjects whose CDAI has not improved by Week 24 are to be discontinued.

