# 9.5.2 Observation/assessment items and the study schedule 9.5.2.1 Study schedule

Table 4 shows the schedule for this clinical trial.

Observations and assessments conducted after the start of IMP administration are scheduled beginning from the start date (Day 1) of IMP administration. If observations/assessments need to be rescheduled for whatever reason during the remission-induction period, they must be conducted within plus or minus 1 day of the scheduled date in Week 1 and thereafter plus or minus 3 days of the scheduled dates up to Week 12. During the rescue period, they must be conducted within plus or minus 1 day of the scheduled date in Week 13 and thereafter plus or minus 3 days of the scheduled dates up to Week 24. During the extension period and post-observation period, they must be conducted within plus or minus 7 days of the scheduled dates ("within plus 7 days" of "70 days after the last IMP administration").

Assessments during the follow-up period are to be scheduled using calendar days counting from the date of the last IMP administration. From the last IMP administration to 2 years thereafter, they must be conducted within plus or minus 1 month of the scheduled dates (example: if the last IMP is administered on 1 November 2019, the scheduled date follow-up would be 1 May 2020; the window in this case would be between 1 April 2020 and 1 June 2020).

Date: 18-Apr-2022 version 11.0 Confidential Page 53 of 80

Table 4 E6011-ET2 Study Schedule (All Subjects)

	Screening period		F	Remission	-induction	period (d	ouble-blii	nd)		
Visit	1	2	3	4	5	6	7	8	9	-
Test/Observation Time	Days -42 to -1 days	Week 0 i	Week 1	Week 2	Week 4	Week 6	Week 8	Week 10	Week 12	Disco ntinua tion j
Allowed deviations	1 days	_	± 1 day	± 3 days	_					
Signing of informed consent a	0									
Demographic characteristics, history of present illness	0									
Past medical history, complications	0									
Inclusion/exclusion criteria check	0	0								
Colonoscopy b	0								0	0
IMP administration c		0	0	0	0	0	0	0	○ k	
Prior treatment and	→									→
concomitant drugs/therapies										
Physical findings	0	0	0	0	0	0	0	0	0	0
Height/weight d	0	0		0	0		0		0	0
Vital signs	0	0	0	0	0		0		0	0
Standard 12-lead ECG	0								0	0
Chest X-ray test	0									
Neurological symptoms e	0								0	0
Anti-JCV antibody test	0									0
Blood CD4 + cell test	0								0	0
Viral test, tuberculosis test	0									

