Pregnancy test f	0	0							0	0
C. difficile toxin test	0									
CDAI, PRO2		00		0	0		0		0	0
Haematology test, blood	0	0	0	0	0	0	0	0	0	0
biochemistry test, urinalysis										
Adverse event	←				l	ı	1	ı		 
Serum E6011 concentration g,		0	0	0	0	0	0	0	0	0
Serum anti-E6011 antibodies		0		0	0		0		0	0
Serum total FKN concentration h		0	0	0	0	0	0	0	0	0
Blood CD16 + monocytes, etc. (FCM) h		0	0	0	0				0	0
Blood CD16 + monocyte, etc. genetic markers h		0	0	0	0				0	0
Faecal calprotectin		0		0	0		0		0	0

- a. A written consent of the subject is required prior to undergoing tests and medication washout as part of the requirements to participate in this clinical trial.
- **b.** Endoscopic evaluations are performed by a centralised review.
- The IMP is to be administered after completing all assessments scheduled for that day (excluding serum E6011 concentration immediately after the end of administration).
- d. Height is measured during the screening period (on Visit 1) only.
  e. If abnormal neurological symptoms are found after IMP administration, the patient must be examined by a neurologist and undergo brain MRI (T1-weighted, FLAIR and diffusion-weighted imaging) within two weeks.
- Pregnancy test is conducted only in female subjects of childbearing potential.
- Blood samples are collected before and immediately after (within 10 minutes of) IMP administration between Week 0 and Week 10.

**h.** Test results are to be retained by the testing laboratories and not to be shared with Principal Investigators, Sub-investigators and trial coordinators until code break. Blood CD16+ monocytes, etc. (FCM) is only conducted in Japanese subjects

- i. Randomisation is to be performed at baseline (before the start of IMP administration in Week 0).
- j. As many specified tests and evaluations as possible should be conducted for the assessment at discontinuation.
- **k.** E6011 to be administered after the transition to the rescue period or Extension period.
- I. PML onset is to be investigated over the phone, etc. at six months, one year, one and a half years, and two years after the final IMP dose.
- m. E6011 not to be administered when discontinuing at Week 24 for a lack of CDAI response.
- n. To be conducted during the Week 24 visit or 28 days after discontinuation only when discontinuing at Week 24 for a lack of CDAI response.

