6.6 Study Windows

Week of evaluation for analysis will be defined in table 1 (similar approach as used in the E6011-J081-101 study).

See Table 1 Study Windows below for reference days:

Table 1 Study Windows

Analysis Visit Number	Analysis Visit	Target	Window	
			Lower	Upper
2	Baseline	1	-	-
3	Week 1	8	5	11
4	Week 2	15	12	18
5	Week 4	29	22	35
6	Week 6	43	36	49
7	Week 8	57	50	63
8	Week 10	71	64	77
9	Week 12	85	78	91
10	Week 13	92	-	95
11	Week 14	99	96	102
12	Week 16	113	106	119
13	Week 18	127	120	133
14	Week 20	141	134	147
15	Week 22	155	148	161
16	Week 24	169	162	175
17	Week 28	197	190	203
18	Week 32	225	218	231
19	Week 36	253	246	259
20	Week 40	281	274	287
21	Week 44	309	302	315
22	Week 48	337	330	343
23	Week 52	365	358	371
24*	Week 56	393	386	399
25*	Week 60	421	414	427
26*	Week 64	449	442	455

*Only for non-responders at week 12

The window for the post observational visit (28 days after completion/discontinuation of the treatment):

- For patients that discontinue treatment, the target day will be 28 days after the discontinuation date and the window will be [discontinuation date+1 , 58].
- For patients that complete the extension period or complete the rescue period but because of a lack of efficacy do not continue to the extension period, the target day will be 28 days after end of extension/rescue period date and the window will be [extension/rescue period end date +1 , 58].

Observation that has the most recent date-time on base date-time is adopted if plural observations exist in the time window.

In case that two or more assessments falling in the same window, the closest in absolute value to the target will be chosen. In case of a tie, the earliest assessment will be considered.

Pre-dose pharmacokinetic blood samples should be collected prior to dosing, no time window is advised for this sample. Post dose pharmacokinetic blood samples should be collected within a 10-minute time window starting from the end of the E6011 infusion.

Biomarker/pharmacogenomic samples should be collected during the following time windows specified below;

- During the remission induction period (all subjects), blood samples should be collected within \pm 1 day during Week 1, and within \pm 3 days during Weeks 2 to 12.
- During the extension period (responders), blood samples should be collected within \pm 7 days during Weeks 16 to 52.

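### SAP 6.6 does not settle which record counts as Week 12, and its Week 12 window admits values taken after open-label E6011 has started

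*SAP*

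**What the plan says.** SAP 6.6 (Study Windows) gives two instructions for the same situation. The first is "Observation that has the most recent date-time on base date-time is adopted if plural observations exist in the time window". The second is "In case that two or more assessments falling in the same window, the closest in absolute value to the target will be chosen", followed by "In case of a tie, the earliest assessment will be considered". The SAP does not define the base date-time, does not give the two sentences separate scopes, and does not say which prevails.

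The window table in the same section (visit number, visit, target, lower, upper) reads "9 Week 12 85 78 91" for Week 12 and "10 Week 13 92 - 95" for Week 13. The dash means that Week 13 has no lower limit.

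Open-label treatment begins at the Week 12 visit. The footnote to the Week 12 dosing entry in protocol Table 4 says "E6011 to be administered after the transition to the rescue period or Extension period", and protocol 9.1 describes rescue as "additional administrations of 10 mg/kg of E6011 in Week 12, Week 13, Week 14", continuing to Week 22. On visit timing, protocol 9.5.2.1 allows 3 days either side of the scheduled date up to Week 12, and then: "During the rescue period, they must be conducted within plus or minus 1 day of the scheduled date in Week 13".

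SAP 4.1 ties baseline to the first dose. There is no matching cut at the other end: SAP 6.1 describes the remission-induction period only as running from day 0 to week 12. SAP 6.1 also says that all outputs by treatment group use the remission-induction assignment.

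**The concern.** Two programmers could each follow SAP 6.6 faithfully and build different Week 12 datasets. That would matter little if every candidate record came from the blinded period. Here the window continues for several days after all continuing subjects, including those on placebo, have received E6011. Because tables keep the randomised label, a placebo subject's value after open-label E6011 could appear as placebo Week 12 data.

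The records most directly at risk are those scheduled at the rescue Week 13 visit: haematology, biochemistry including CRP, urinalysis, vital signs, physical findings and serum E6011. CDAI and PRO2 are not scheduled then. A CDAI could enter only if it was unscheduled or taken at discontinuation, after the Week 12 dose and by Day 91.

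**Working it through.** **Inputs.** Day 1 is the first dose (protocol 9.5.2.1), so the target for Week w is Day 7w + 1.

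- Week 12: 7 × 12 + 1 = Day 85. Permitted visit 85 ± 3 = Days 82-88. SAP window Days 78-91.
- Week 13: 7 × 13 + 1 = Day 92. Permitted visit 92 ± 1 = Days 91-93. SAP window: no lower limit, upper Day 95.
- Next scheduled CDAI: Week 14 in rescue, Day 99 ± 3 = Days 96-102; Week 16 in extension, Day 113 ± 7 = Days 106-120. Both lie beyond Day 91.

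**Which record each rule selects.** Assume that the first open-label dose is given on the day of the Week 12 visit, and that one further value exists on a later day up to Day 91. The latest-value reading always takes the later record. The closest rule takes it only if its distance from Day 85 is smaller; ties go to the earlier record.

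| Week 12 visit | Distance from Day 85 | Later days in window | Latest takes post-dose value | Closest takes post-dose value |
|---|---|---|---|---|
| Day 82 | 3 | 9 | 9 | 5 (Days 83-87) |
| Day 83 | 2 | 8 | 8 | 3 (Days 84-86) |
| Day 84 | 1 | 7 | 7 | 1 (Day 85) |
| Day 85 | 0 | 6 | 6 | 0 |
| Day 86 | 1 | 5 | 5 | 0 |
| Day 87 | 2 | 4 | 4 | 0 |
| Day 88 | 3 | 3 | 3 | 0 |
| Total | | 42 | 42 | 9 |

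The rules give different answers in 42 − 9 = 33 of these 42 pairs. Over the whole 14-day window there are 14 × 13 / 2 = 91 pairs. The closest rule takes the later value in 49, so the rules differ in 91 − 49 = 42. These are counts of possible day pairs, not frequencies.

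**A Week 13 visit on Day 91.** Its distance from the Week 12 target is 91 − 85 = 6, against at most 3 for a permitted Week 12 visit. If Day 91 is assigned to Week 12, the latest-value reading always selects it. The closest rule never does, unless the Week 12 value is missing. The table does not settle whether Day 91 belongs to Week 12 or Week 13.

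**With a pre-dose cut.** If Week 12 admits only values before the first open-label dose, the number of post-dose selections is 0 under either rule.

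**What one changed CDAI could do.** The decision rule in protocol 9.7.1.6.1 needs a posterior probability of at least 0.50 that the difference in CR100 rates is 25 points or more; SAP 6.8.1 gives Beta(1/2, 1/2) priors. As a check on the calculation, the plan's own figure was reproduced first. With 20 per group and a true difference of 40 points, the probability of confirming efficacy is 0.807 to 0.874 for assumed placebo rates of 5% to 60%, which agrees with the stated figure of above 80%. Protocol 9.7.2 reports 25 enrolled. The split is not given, so 13 on E6011 and 12 on placebo is assumed:

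| Responders, E6011 vs placebo | Posterior probability | Efficacy confirmed |
|---|---|---|
| 6 vs 2 | 0.562 | yes |
| 6 vs 3 | 0.386 | no |
| 7 vs 3 | 0.549 | yes |
| 7 vs 4 | 0.380 | no |

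Near the threshold, one placebo subject reclassified by a post-dose CDAI would change the conclusion.

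**The case against.** **The first rule may be poor English rather than a second rule.** If the base date-time means the target day, the sentence says nearest to the reference, and the next sentence repeats it with a tie-break. This is possible, and the section does call its table a list of reference days. But the SAP does not define the term. Under that reading the conflict largely disappears; the 9 pairs under the closest rule and the missing-value case do not.

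**Day 91 is not clearly a Week 12 day.** This stands. A reader might infer that a Day 91 visit plainly falls into Week 12. The blank lower limit means that the table does not say so, and Day 91 is only 1 day from the Week 13 target. The defect is an unassigned day.

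**The route to the primary endpoint is narrow.** This also stands. A reader might infer that CR100 is routinely contaminated. The schedule does not support that: no CDAI is planned between the Week 12 visit and Day 96. An extra or discontinuation CDAI inside the window is needed.

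**Trial conduct gives some protection.** Week 12 data must be entered before the first rescue or extension evaluation (protocol 9.1), and the remission-induction database is locked and analysed separately (protocol 9.7). This may keep later records out in practice, but neither step is a rule for selecting records. The entire-administration analysis pools the periods and has no other window table.

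**Concentration tables may be partly shielded.** SAP 5.3 limits the pharmacokinetic set to subjects who took active treatment. Whether placebo subjects enter once they receive open-label E6011 is not stated. Safety laboratory values and vital signs use the safety set and have no such limit.

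**Conclusion.** The point holds in a limited form. SAP 6.6 contains two selection rules that conflict if read literally, with an undefined reference point and no precedence. Independently of that, nothing restricts Week 12 to records taken before open-label E6011. A post-dose value can be reported as double-blind Week 12 data in three ways: under the latest-value reading, whenever a later in-window value exists (42 of 42 pairs); under the closest rule, when the Week 12 visit was on Days 82-84 and a later value is nearer Day 85 (9 of 42); and under either rule, when the Week 12 value is missing.

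A reader might also infer that only the first rule is at fault and that deleting it is enough. The 9 pairs and the missing-value case show that it is not.

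The scheduled exposure is confined to Week 12 non-responders seen for Week 13 on Day 91, one of three permitted days, and to descriptive summaries. The exposure of the primary endpoint is indirect, though at 25 subjects one record could decide the result. These conclusions assume that the open-label dose is given on the Week 12 visit day; the posterior figures also assume a 13/12 split. The documents do not show how often such records occurred. This should be corrected before lock; it does not call the design or sample size into question.

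**What to change.** Make three edits to SAP 6.6 before the remission-induction database is locked and unblinded, so that the choice cannot depend on results:

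1. Keep one selection rule, closest to target with the earliest taken if tied, and delete the sentence about the most recent date-time.
2. State that a Week 12 value is eligible only if it was collected before the subject's first open-label E6011 dose. This covers CDAI, PRO2, laboratory values, vital signs and concentrations, and applies in the entire-administration analysis too.
3. Define the lower limit of the Week 13 window as the first record after that dose. A fixed lower limit of Day 91 would not do: with the pre-dose restriction, post-dose Days 89 and 90 would have no window.

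The cost is a few sentences and the Week 12 and Week 13 rows of the window table, plus the matching change to the programming specification. No new data are needed, and the design, sample size, visit schedule and treatment are untouched.

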6.6.1 Pharmacokinetic Sampling

Blood samples for the determination of serum E6011 concentrations are to be collected pre-dose and post the end of the infusion (within 10 minutes of the end of the infusion from week 0 to week 10).

Blood samples will be collected as follows;

For all subjects during the remission-induction period blood samples will be collected during weeks 0, 1, 2, 4, 6, 8, 10, 12 and upon discontinuation.

During the extension period (responders) blood samples will be collected during weeks 16, 20, 24, 28, 32, 36, 40, 44, 48, 52 and upon discontinuation.

During the rescue period (non-responders) blood samples will be collected during weeks 13, 14, 16, 18, 20, 22, 24 and upon discontinuation.

During the extension period (non-responders) blood samples will be collected during weeks 28, 32, 36, 40, 44, 48, 52, 56, 60, 64 and upon discontinuation.

6.6.2 Biomarker Sampling

Blood samples for the determination of serum total FKN concentrations are to be collected as follows;

For All subjects during the remission-induction period blood samples will be collected during weeks 0, 1, 2, 4, 6, 8, 10, 12 and upon discontinuation.

Faecal samples for the determination of faecal calprotectin concentrations are to be collected as follows;

For All subjects during the remission-induction period faecal samples will be collected during weeks 0, 2, 4, 8, 12 and upon discontinuation.

During the extension period (responders) faecal samples will be collected during weeks 16, 20, 24, 28, 32, 36, 40, 44, 48, 52 and upon discontinuation.

During the rescue period (non-responders) faecal samples will be collected during weeks 14, 16, 20, 24 and upon discontinuation.

During the extension period (non-responders) faecal samples will be collected during weeks 28, 32, 36, 40, 44, 48, 52, 56, 60, 64 and upon discontinuation.

Blood samples for the determination of serum CRP concentrations are to be collected as follows;

For All subjects during the remission-induction period blood samples will be collected during weeks 0, 1, 2, 4, 6, 8, 10, 12 and upon discontinuation.

During the extension period (responders) blood samples will be collected during weeks 16, 20, 24, 28, 32, 36, 40, 44, 48, 52 and upon discontinuation.

During the rescue period (non – responders) blood samples will be collected during weeks 13, 14, 16, 18, 20, 22, 24 and upon discontinuation.

During the extension period (non-responders) blood samples will be collected during weeks 28, 32, 36, 40, 44, 48, 52, 56, 60, 64 and upon discontinuation.

6.6.3 Immunogenicity Sampling

Blood samples for the determination of Anti-E6011 antibodies are to be collected as follows;

For All subjects during the remission-induction period blood samples will be collected during weeks 0, 2, 4, 8, 12 and upon discontinuation.

During the extension period (responders) blood samples will be collected during weeks 16, 20, 24, 28, 32, 36, 40, 44, 48, 52 and upon discontinuation.

During the rescue period (non-responders) blood samples will be collected during weeks 14, 16, 20, 24 and upon discontinuation.

During the extension period (non-responders) blood samples will be collected during weeks 28, 32, 36, 40, 44, 48, 52, 56, 60, 64 and upon discontinuation.

6.7 Study Medication

The concomitant use of the following drugs/treatments shall be prohibited until the end of the extension period (or discontinuation):

Prohibited concomitant drugs	Generic name	ATC Code	Administration route
Biologics	Adalimumab	L04AB	
	Infliximab	L04AB	
	Ustekinumab	L04AC	
	Certolizumab pegol	L04AB	
	Natalizumab	L04AA	
	Vedolizumab	L04AA	
Adrenocorticosteroids injection/enema preparation	Dexamethasone	C05AA H02AB	Intravenous drip Intravenous bonus Subcutaneous Intramuscular Rectal
	Triamcinolone	C05AA H02AB	Intravenous drip Intravenous bonus Subcutaneous Intramuscular Rectal
	Hydrocortisone	A07EA C05AA H02AB	Intravenous drip Intravenous bonus Subcutaneous Intramuscular Rectal
	Prednisolone	H02AB H02BX	Intravenous drip Intravenous bonus

		A07EA C05AA	Subcutaneous Intramuscular Rectal
	Batamethasone	A07EA C05AA H02AB	Intravenous drip Intravenous bonus Subcutaneous Intramuscular Rectal
	Methylprednisolone	H02AB H02BX	Intravenous drip Intravenous bonus Subcutaneous Intramuscular Rectal
	Budesonide	A07EA	Intravenous drip Intravenous bonus Subcutaneous Intramuscular Rectal
Adrenocorticosteroids suppository	Diflucortolone	D07XC D07AC D07BC For diflucortolone there are only entries for ATC D (dermatological treatment)	Rectal
	Hydrocortisone	A07EA C05AA H02AB	Rectal
	Batamethasone	A07EA C05AA H02AB	Rectal
Immunomodulators (Except for topical use)	Cyclosporin	L04AD	Oral Sublingual Intravenous drip Intravenous bonus Subcutaneous Intramuscular Rectal Respiratory (Inhalation) Transdermal
	Tacrolimus hydrate	L04AD	Oral Sublingual Intravenous drip Intravenous bonus Subcutaneous Intramuscular Rectal Respiratory (Inhalation)

			Transdermal
	Mycophenolate mofetil	I04AA	Oral Sublingual Intravenous drip Intravenous bonus Subcutaneous Intramuscular Rectal Respiratory (Inhalation) Transdermal
Immunoglobulin products (Immunoglobulin preparations: J06B) or blood products	(Whole blood products)	B05A (blood and related products)	
	(Blood component products)	B05AA (blood substitutes and plasma protein fractions) B02BD (blood coagulation factors)	
	(Blood plasma fraction products)	B05AA B05AX	
Live vaccines	(Yellow fever)	I07BL	
	(Mumps)	I07BE I07BJ I07BD	
	(Tuberculosis)	I07AN	
	(Chicken pox)	I07BX	
	(Rubella)	I07BJ I07BD	
	(Measles)	I07BD	
	(Measles-rubella combination)	I07BD	
	(Rotavirus)	I07BH	
Investigational drug	(All investigational drugs)		

Extent of investigational medicinal product exposure and compliance.

Duration of IMP exposure is defined as date and time of last IMP administration – date and time of first double-blind IMP administration + 14 days, regardless of unplanned intermittent discontinuations.

Duration will be presented in days.

Duration of IMP exposure will be summarized descriptively as a quantitative variable (number, mean, SD, median, minimum, and maximum). In addition, duration of treatment exposure will also be summarized categorically by numbers and percentages for each of the following categories and

cumulatively according to these categories: ≤ 1 week, (1 week, 4 weeks], (4 weeks, 8 weeks], (8 weeks, 12 weeks], (12 weeks, 22 weeks], (22 weeks, 48 weeks], (48 weeks, 60 weeks], >60 weeks.

Compliance:

A given administration will be considered non-compliant if the patient did not take the planned dose of treatment as required by the protocol. No imputation will be made for patients with missing or incomplete data. The percentage of noncompliant administrations will be descriptively summarized by treatment. Percentage of noncompliant administrations is defined as number of non-compliant administrations divided by the number of total administrations.

Treatment compliance (%) by period is defined as the actual number of IMP administration divided to the planned number of administrations.

Treatment compliance will be summarized by descriptive statistics for the FAS populations by treatment and study period. In addition, the percentage of patients per compliance level will be also summarized: $\leq 60\%$, (60%, 80%], (80%, 100%].

